#### Administrative Supplement Power Estimation:

Given the early-stage nature of the proposed supplementary research, we do not anticipate adequate power to detect clinically meaningful differences for our primary and several secondary outcomes for Hispanic / Latino dyads alone. However, it is possible to detect promising trends in some secondary outcomes that had a large effect size in our pilot study.

We anticipate using this supplementary grant to collect the pilot data for effectiveness of our intervention in the key outcomes of our interest in this particular population.

#### 9.3 POPULATIONS FOR ANALYSES

N/A

#### 9.4 STATISTICAL ANALYSES

##### 9.4.1 GENERAL APPROACH

**Analysis:** Descriptive analyses of variables will examine distributions, influential data points, and missing data. Means (standard deviations) will be reported for continuous variables and frequencies (percentages) for categorical variables. Continuous variables (e.g., PC Domain Index, etc) that are poorly distributed may be transformed or analyzed using non-parametric

tests. We anticipate missing data on independent variables will be minimal. We will use simple mean and mode imputation for those variables included in regression models if less than 5% of patients have missing data; else, conditional (i.e., regression) imputation will be used. Available case analysis will be conducted for 30-day outcomes. Missing 60-day dichotomous outcomes will be multiply imputed if missingness exceeds 10%. Caregiver data collection is completed after deaths as in our prior ADRD research. Primary analysis will use intention-to-treat analysis. We will evaluate the effectiveness of randomization by comparing intervention and control participants on baseline measures. Variables that are not equally distributed between arms could potentially bias results. We will include these variables in each initial model and use a change-in-effect method for determining whether they are confounders. If removing any of these variables from the model does not appreciably change the regression coefficient estimate of the intervention group variable, we will not need to include them in the final model. Given our randomized design, we anticipate little confounding. A priori exploratory analyses will examine effects by sex as a biological variable, race / ethnicity, and GDS stage.

---

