## SCHEMA

## Flow Diagram

## 1.2 SCHEDULE OF ACTIVITIES

|  | Visit 1: During Hospitalization | Visit 2: During Hospitalization (Intervention) | Visit 3: PC Call 72 hours after discharge (Intervention) | Visit 4: PC Call 2 weeks after discharge (Intervention) | Visit 5 CRC interview 30 days post Hospitalization | Visit 6 CRC interview 60 days post hospitalization | CRC EHR Review post-60-day Hospitalization |
|--|---------------------------------|--|--|---|--|--|--|
| STUDY ENROLLMENT ACTIVITIES                                   |                                 |  |  |   |  |  |  |
| EHR Eligibility Screen   | X                               |  |  |   |  |  |  |
| Informed Consent   | X                               |  |  |   |  |  |  |
| Enrollment Baseline Assessment                                       | X                               |  |  |   |  |  |  |
| Randomization  | X                               |  |  |   |  |  |  |
| Control arm  | X                               |  |  |   | X  | X  | X  |
| ADRD-PC intervention arm   | X                               | X  | X  | X   | X  | X  | X  |
| DATA COLLECTION ACTIVITIES                                    |                                 |  |  |   |  |  |  |
| Hospital / ED transfers  |                                 |  |  |   | X  | X  | X  |
| Palliative Care Domain Index   |                                 |  |  |   |  |  | X  |
| Symptom Management at the End of Life in Dementia (SM-EOLD)          |                                 |  |  |   | X  | X  |  |
| Neuropsychiatric Inventory Questionnaire (NPI-Q)                     |                                 |  |  |   | X  | X  |  |
| Post-acute use of palliative care, hospice                           |                                 |  |  |   | X  | X  |  |
| New NH transition  |                                 |  |  |   |  |  | X  |
| Documented discussion of dementia prognosis                          |                                 |  |  |   |  |  | X  |
| Documented decision-making for goals of care                         |                                 |  |  |   |  |  | X  |
| Shared decision-making about hospitalization & burdensome treatments |                                 |  |  |   | X  | X  |  |
| Family Distress in Advanced Dementia scale                           |                                 |  |  |   | X  | X  |  |
| Zarit Burden scale   |                                 |  |  |   | X  | X  |  |

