Analysis to Meet Aim 1: We will compare control and intervention arms on hospital transfers (primary outcome) during 60 days post-discharge. This count outcome is defined as the total number of emergency room visits plus hospital admissions per at-risk patient-days. We will use Poisson regression with empirical 'robust' standard errors allowing for overdispersion to compare the transfer rates between groups. We will use the length of follow-up as the offset variable, which means that patients who have data only from the 30-day interview will be included. The primary analysis will be based on the model with main effects for treatment group, study site, GDS Stage and patient and caregiver sex as biological variables. Evaluation of the treatment effect will be based on a Wald test. The covariate-adjusted treatment effect will be quantified as an incidence rate ratio (IRR) with a 95% confidence interval. Considering that over 60% of patients in the pilot study did not have any hospital transfers, we will conduct a sensitivity analysis for the treatment effect on 60-day hospital transfers with a marginalized zero-inflated Poisson (MZIP) model, which may modestly increase power. Secondary Poisson and MZIP analyses will compare study arms for 30-day hospital transfer rates. An exploratory analysis will be conducted to examine interactions of treatment group with study site, sex, race / ethnicity and GDS Stage, respectively, on 60-day hospital transfers. While the proposed study is powered to detect whether or not ADRD-PC is effective, a much larger study would be needed to have adequate power to detect differences by sex or GDS Stage and would be justifiable only after the completion of this initial trial. An interaction model will be used if an omnibus test for interactions is statistically significant at the 0.05 level. A second exploratory analysis will evaluate a dose-response effect of the intervention on the hospital transfer rate. A dose for patients receiving the intervention is defined as the number of key intervention components used in fidelity monitoring (range 0 to 4 with 0 for controls). The dose effect is the incremental benefit of adding a single component; its rescaling gives the per-protocol effect of the full intervention.

---

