#### 9.4.3 ANALYSIS OF THE SECONDARY ENDPOINT(S)

**Aim 2:** To compare patient-centered secondary outcomes between intervention and control arms: a) symptom treatment (Palliative Care Domain index); b) symptom control (Symptom Management at the End of Life in Dementia scale, Neuropsychiatric Inventory Questionnaire); c) post-acute use of palliative care or hospice; and d) transition to nursing home care.

Analysis to Meet Aim 2: We will compare study arms during 60 days post-discharge on the following outcomes:

2.a. Symptom treatment: This ordinal outcome is the summation of presence (=1) or absence (=0) of 10 domains of palliative care. We will treat it as a continuous variable due to a high variation observed in the pilot data. We will use Student's t-test to compare the mean difference between study arms unless violation of assumptions warrants the Mann-Whitney test. We will use a multiple linear regression model with main effects for treatment group, study site, GDS Stage and patient and caregiver sex as a biological variable.

2.b. Symptom control: We will use Symptom Management (SM-EOLD) scale to measure caregiver report of patients' uncontrolled symptom distress and Neuropsychiatric Inventory Questionnaire (NPI-Q) to measure caregiver report of patients' neuropsychiatric symptom distress. Linear mixed models with random intercepts for patients will be used with a time indicator (30 vs 60 days follow-up) with the above main effects.

2.c. Use of post-acute palliative care or hospice: This outcome will be defined by whether patients ever use hospice or outpatient palliative care during the time from discharge to 60 days follow-up. We will compare the proportions using Pearson's chi-square test. Logistic regression will be used for multivariable modeling with the same main effects as in Aim 2.a. Final estimates will be reported as covariate-adjusted odds ratios.

2.d. Transition to nursing home care: This outcome will be defined by whether patients transition to nursing home care during the time from discharge to 60 days follow-up. We will compare proportions using Pearson's chi-square test. Logistic regression will be used for multivariable modeling with the same main effects as in Aim 1. Final estimates will be reported as covariate-adjusted odds ratios.

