**Aim 3:** To compare caregiver-centered secondary outcomes between intervention and control arms: a) communication about prognosis and goals of care; b) shared decision-making; and c) caregiver distress (Family Distress in Advanced Dementia scale, Zarit Burden interview).

Analysis to Meet Aim 3: For the dichotomous outcome variables pertaining to communication (hypothesis 3a) and shared decision-making (hypothesis 3b), Pearson's chi-square test will test for differences in proportions between study arms. We will use logistic regression for the multivariable modeling. Treatment effect estimates will be reported as adjusted odds ratios. To test hypothesis 3c, we will use Student's t-test for mean difference since the outcome, Family Distress in Advanced Dementia (FDAD), is continuous. Linear mixed models as described for Aim 2.b. above will be used to test treatment effects for 30-day and 60-day outcomes jointly.

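### Does the loosely worded baseline-imbalance rule in section 9.4.1 leave the primary model and the Aim 3 models open to choice?

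*Combined protocol and SAP*

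**What the plan says.** Section 9.4.1 sets up the screen: "We will evaluate the effectiveness of randomization by comparing intervention and control participants on baseline measures". For variables that turn out unequal it continues: "We will include these variables in each initial model and use a change-in-effect method for determining whether they are confounders". A variable may then be left out of the final model on this condition: "If removing any of these variables from the model does not appreciably change the regression coefficient estimate of the intervention group variable". The Administrative Supplement Analysis in 9.4.3 repeats the rule. Neither place names the variables, says how unequal is unequal, or gives a percentage for the change. Section 1.2 lists only an "Enrollment Baseline Assessment", without items.

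The outcome-specific sections are more definite. Section 9.4.2 states: "The primary analysis will be based on the model with main effects for treatment group, study site, GDS Stage and patient and caregiver sex". It then attaches the Wald test and the adjusted rate ratio to that model. In 9.4.3, Aims 2.a to 2.c use the same effects, and for 2.d: "Logistic regression will be used for multivariable modeling with the same main effects as in Aim 1". For Aim 3c, "Linear mixed models as described for Aim 2.b. above will be used to test treatment effects", so the covariates carry over. For Aims 3a and 3b the test is Pearson's chi-square, followed by: "We will use logistic regression for the multivariable modeling. Treatment effect estimates will be reported as adjusted odds ratios". No covariates are named there.

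**The concern.** Choosing covariates by how far they move the treatment coefficient lets the fitted effect help choose the model. The wording of 9.4.1 reaches every initial model and exempts none, and no sentence puts the rule below the fixed sets in 9.4.2 and Aim 2. Two analysts could therefore follow the text and report different primary rate ratios. An analyst who could report whichever model looked better would exceed the 5% error rate. For the logistic models of Aims 3a and 3b the gap is plainer, because the general rule is the only explicit covariate guidance. At stake are the reproducibility of the primary estimate and, in the worst case, its type I error.

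**Working it through.** **1. Which text governs each outcome**

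| Outcome | Named test or model | Covariates named? |
|---|---|---|
| Aim 1 | Robust Poisson, Wald test | Yes (9.4.2) |
| 2.a | t-test; linear model | Test needs none; model yes |
| 2.b | Mixed model | Yes |
| 2.c, 2.d | Chi-square; logistic | Test needs none; model yes |
| 3a, 3b | Chi-square; logistic | Test needs none; model no |
| 3c | t-test; mixed model | Test needs none; model inherits 2.b |

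The only outcomes with no covariate set are 3a and 3b, and only for the odds ratios that accompany an unadjusted test.

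**2. The plan's own power figures**

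Primary outcome, 180 per arm, rates 0.53 and 0.33 (ratio 0.33/0.53 = 0.62):

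Power = Φ( ln(0.53/0.33) / √{φ[1/(180×0.53) + 1/(180×0.33)]} − 1.96 ).

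- φ = 1: 0.4738/0.1653 − 1.96 = 0.91, power 0.818 (Table 3: 0.82).
- φ = 1.65: 0.4738/0.2123 − 1.96 = 0.27, power 0.607 (Table 3, overdispersed: 0.60). The factor 1.65 is inferred, not stated. It also gives 0.814, 0.765 and 0.555 against the other three overdispersed entries of 0.81, 0.76 and 0.55.

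Aim 3a, unadjusted comparison of two proportions:

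Power = Φ( {Δ − 1.96√[2p̄(1−p̄)/n]} / √{[p₁(1−p₁)+p₂(1−p₂)]/n} ).

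- Goals of care, 25% v 39%: 0.815 and 0.766 at n = 180 and 159 (Table 3: 0.82, 0.77).
- Prognosis, 3% v 11%: 0.848 and 0.801 (Table 3: 0.85, 0.80).

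These entries match a test with no covariates, which agrees with the chi-square being the planned test for 3a.

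**3. What the rule does to the primary analysis**

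The simulation used the 9.4.2 model with its covariates always kept, 180 dyads per arm, control rate 0.53, and full 60-day follow-up. The rest is assumed, because the documents give no values: 6, 12 or 20 independent candidates, half of them prognostic (log-rate 0.20 to 0.25 per SD); entry by t-test at p<0.05 or p<0.10; and backward removal while the treatment log coefficient stays within 10% of its initial value. Overdispersion was set so that fixed-model power is about 62%. There were 12,000 to 20,000 trials per setting and rate ratio. All results are percentages.

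| Candidates, entry p | Type I: fixed | rule | either | Verdict differs, null | Power: fixed | rule | Verdict differs, IRR 0.62 |
|---|---|---|---|---|---|---|---|
| 6, 0.05 | 5.66 | 5.58 | 5.87 | 0.49 | 62.4 | 62.6 | 1.64 |
| 6, 0.10 | 5.66 | 5.42 | 5.98 | 0.88 | 62.4 | 62.6 | 2.28 |
| 12, 0.05 | 5.70 | 5.39 | 6.08 | 1.06 | 61.8 | 62.0 | 2.54 |
| 12, 0.10 | 5.70 | 5.29 | 6.26 | 1.53 | 61.8 | 62.1 | 4.07 |
| 20, 0.05 | 5.83 | 5.73 | 6.34 | 1.12 | 62.0 | 61.7 | 3.21 |
| 20, 0.10 | 5.83 | 5.71 | 6.65 | 1.76 | 62.0 | 61.7 | 4.80 |

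The columns check one another: either = (fixed + rule + verdict differs)/2. For 12 candidates at p<0.10, (5.70 + 5.29 + 1.53)/2 = 6.26.

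- Rule minus fixed, type I error: −0.08 to −0.41 points.
- Either minus fixed: 5.87 − 5.66 = 0.21 up to 6.65 − 5.83 = 0.82 points.
- Rule minus fixed, power: −0.3 to +0.3 points.

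Monte Carlo standard error is about 0.2 points (null) and 0.3 to 0.4 points (power); paired differences are tighter. A separately written run of the central setting (12 candidates, p<0.10; 4,000 trials per rate ratio) gave type I error of 5.9% fixed, 5.7% rule and 6.7% either, and power of 62.8% and 62.3%.

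The final model differs from 9.4.2 in 20% to 72% of null trials and 11% to 40% at IRR 0.62. These shares follow from the assumed settings and do not predict this trial. The null share is high because a 10% change is taken against a coefficient near zero. When the model differs, the median shift in the rate ratio is 4 to 5% (null) or 6 to 7% (IRR 0.62; 0.62 × 0.065 is about 0.04).

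**4. Aims 3a and 3b**

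A null logistic simulation assumed 360 dyads, about a 25% event rate, 10 candidates (3 prognostic, log odds ratio 0.5 per SD) and 1,500 runs. Four versions of the rule, each fixed in advance, had type I error of 4.4% to 4.7%, against 5.1% unadjusted. Picking the most favourable of the five gave 6.3% (standard error about 0.6 points). The log odds ratio varied across the five by a median of 0.06, a factor of e^0.06 = 1.06.

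**The case for a change.** The best case for a change is that the specific-over-general reading is an inference. Section 9.4.1 speaks of every initial model and of a final model, and the supplement sets the rule and the fixed primary model side by side without ranking them. Treating the rule as an addition to the fixed set is therefore tenable. The Aim 3 gap does not depend on that reading, and a change-in-coefficient test suits logistic models poorly: odds ratios are non-collapsible, so a prognostic variable can move the coefficient without any confounding. The cure would be a line or two of wording.

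The textual gap stands. Its reach is short. Section 9.4.2 says which model the primary analysis rests on and hangs the test and estimate on it, so a different primary rate ratio needs the less natural reading. For 3a and 3b, if the rule were really the only source of covariates, a balanced trial would have nothing to adjust for and the promised adjusted odds ratios would be empty. The coherent reading is a dropped cross-reference to the Aim 2 set. Non-collapsibility affects only those supporting estimates, since the chi-square tests use no covariates. The supplement is a 50-dyad pilot that section 9.2 does not claim is adequately powered. Section 6.3 keeps the principal investigator masked through analysis; that does not show the analyst is masked, so it counts for little here.

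**Conclusion.** No change follows. The rule in 9.4.1 lacks detail, but the primary analysis and the Aim 2 models are specified where they are described, and the Aim 3a and 3b tests cannot be touched by covariate choice. Analysts would reasonably use the Aim 2 covariates for the Aim 3 odds ratios. Even if the rule were applied to the primary model, type I error was 0.1 to 0.4 points below the fixed model and power was within 0.3 points. Open choice between the two models cost at most 0.8 points of type I error. The significance verdict differed in 0.5 to 1.8% of null trials and 1.6 to 4.8% at a rate ratio of 0.62. These sizes rest on assumed candidates, prognostic strengths, entry thresholds, a 10% cut-off and complete follow-up. The conclusion rests mainly on the text of 9.4.2 and 9.4.3, and the simulations show that little is lost if that reading is not followed.

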#### 9.4.2 ANALYSIS OF THE PRIMARY ENDPOINT(S)

**Aim 1:** *To conduct a multi-site RCT of the ADRD-PC program of dementia-specific palliative and transitional care (**intervention arm**) vs publicly available educational material for dementia caregivers (**control arm**) to compare 60-day hospital transfers (hospitalization and emergency room visits) for persons with late-stage ADRD (**primary outcome**).*

Analysis to Meet Aim 1: We will compare control and intervention arms on hospital transfers (primary outcome) during 60 days post-discharge. This count outcome is defined as the total number of emergency room visits plus hospital admissions per at-risk patient-days. We will use Poisson regression with empirical 'robust' standard errors allowing for overdispersion to compare the transfer rates between groups. We will use the length of follow-up as the offset variable, which means that patients who have data only from the 30-day interview will be included. The primary analysis will be based on the model with main effects for treatment group, study site, GDS Stage and patient and caregiver sex as biological variables. Evaluation of the treatment effect will be based on a Wald test. The covariate-adjusted treatment effect will be quantified as an incidence rate ratio (IRR) with a 95% confidence interval. Considering that over 60% of patients in the pilot study did not have any hospital transfers, we will conduct a sensitivity analysis for the treatment effect on 60-day hospital transfers with a marginalized zero-inflated Poisson (MZIP) model, which may modestly increase power. Secondary Poisson and MZIP analyses will compare study arms for 30-day hospital transfer rates. An exploratory analysis will be conducted to examine interactions of treatment group with study site, sex, race / ethnicity and GDS Stage, respectively, on 60-day hospital transfers. While the proposed study is powered to detect whether or not ADRD-PC is effective, a much larger study would be needed to have adequate power to detect differences by sex or GDS Stage and would be justifiable only after the completion of this initial trial. An interaction model will be used if an omnibus test for interactions is statistically significant at the 0.05 level. A second exploratory analysis will evaluate a dose-response effect of the intervention on the hospital transfer rate. A dose for patients receiving the intervention is defined as the number of key intervention components used in fidelity monitoring (range 0 to 4 with 0 for controls). The dose effect is the incremental benefit of adding a single component; its rescaling gives the per-protocol effect of the full intervention.

---

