## 3 OBJECTIVES AND ENDPOINT / OUTCOMES

| OBJECTIVES  | ENDPOINT / OUTCOMES   | JUSTIFICATION   |
|---|---|---|
| Primary   |   |   |
| To conduct a multi-site RCT of the ADRD Palliative Care (ADRD-PC) program of dementia-specific palliative and transitional care ( intervention arm ) vs publicly available educational material for dementia caregivers ( control arm ) to compare 60-day hospital transfers (hospitalization and | Number of emergency room visits + hospital admissions within 60 days after discharge from index hospitalization | Hospital transfers are common for persons with late-stage ADRD, and are burdensome and stressful for the person and their family caregivers. Evidence shows that some hospital transfers are avoidable because acute illness can be treated in lower intensity settings, OR because goals of care are more comfort-focused. |

| OBJECTIVES   | ENDPOINT / OUTCOMES   | JUSTIFICATION   |
|--|---|---|
| emergency room visits) for persons with late-stage ADRD ( primary outcome ).

Secondary |   |   |
| To compare patient-centered secondary outcomes between intervention and control arms                 | a) Palliative Care Domain Index
b) Symptom Management at End of Life in Dementia
c) Neuropsychiatric Inventory Questionnaire
d) Post-acute use of palliative care, hospice
e) NH transitions                      | Physical and neuropsychiatric symptom distress is common in late-stage ADRD, and worsens toward death. Post-acute access to palliative services can improve outcomes, while new nursing home transitions may be avoidable with added community-based services and supports. |
| To compare caregiver-centered secondary outcomes between intervention and control arms               | a) documented communication about prognosis and goal of care
b) shared-decision making about hospitalization and other major treatment decisions
c) Family Distress in Advanced Dementia scale
d) Zarit Burden scale | Family caregivers serve as surrogate decision-makers in late-stage ADRD. They experience poor quality communication in usual care. In addition, caregivers experience significant emotional strain relative to caregiving role.   |

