## 5.3 STRATEGIES FOR RECRUITMENT AND RETENTION

Recruitment and retention of seriously ill patients with stressed caregivers is challenging, and can threaten validity. We will train all sites in the Palliative Care Research Collaborative best practices to assure compliance with research ethics standards, complete and timely case-finding, compassionate approach and messaging, and flexibility to accommodate caregivers.

Participant screening: Site-CRCs will use an EHR algorithm for rapid case-finding. This method, developed during the pilot research, generates daily automated EHR lists of newly hospitalized patients with ADRD. Site-CRCs will conduct brief chart reviews under a HIPAA waiver to confirm eligibility criteria and forward patients with probable late-stage ADRD to the Site-PI for review. After brief EHR reviews by Site-CRCs and Site-PIs to confirm eligibility, Site-PIs will contact the inpatient attending physicians. They will confirm GDS stage as 5, 6 or 7, and seek permission to approach caregivers.

Recruitment and informed consent: Recruitment will utilize diverse communication approaches with family caregivers; these approaches are identical to clinical communication used with family caregivers for people with dementia who lack decisional capacity. Since family caregivers may be present in hospital, or may be barred from visitation due to COVID-19 restrictions and safety concerns, or may live at a great distance from the hospital, recruitment and enrollment procedures will include both in-person and telephone / virtual communication methods. Further, flexibility of communication is essential for the enrollment of the project number of participants, because study enrollment and participation in the ADRD-PC intervention must both occur during acute illness hospitalization.

Site-CRCs will introduce the study to eligible family caregivers using scripted telephone calls or in-person visits. When the Site-CRC conducts recruitment and enrollment via telephone, the Site-CRC will ask if the individual is in a private location, and feels comfortable talking about the study at that time; they will schedule an alternative time if necessary. The Site-CRC will explain the study over the phone using a telephone script. Spanish-speaking CRCs will introduce and explain the study to any Spanish-speaking participants using translated recruitment scripts and study materials.

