## 8 STUDY ASSESSMENTS AND PROCEDURES

## 8.1 ENDPOINT AND OTHER NON-SAFETY ASSESSMENTS

Data collection will be identical for both arms. Data will be obtained from caregiver enrollment interviews and 30- and 60-day interviews post-discharge, and from electronic health record (EHR) reviews encompassing the 60-day period post-hospitalization. Based on the pilot RCT, we estimate 10% of persons with late-stage ADRD will die during follow-up; caregiver interview data collection will proceed using a Bereavement Interview adaptation. Outcome measures will focus on 60-day interviews; 30-day interim interviews are necessary to support retention, ensure data capture for persons with ADRD who die, and for valid recall of hospital transfers (primary outcome) and secondary outcomes.

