### **Family Caregiver Interviews:**

1. Emergency room visits + hospital admissions after discharge from index hospitalization
2. Use of hospice or community palliative care services
3. Patient symptom distress
  - a. Instrument: Symptom Management at the End of Life in Dementia (SM-EOLD)
  - b. Instrument: Neuropsychiatric Inventory Questionnaire (NPI-Q)
4. Shared decision-making about hospitalization
5. Shared decision-making about other burdensome treatments
6. Caregiver distress
  - a. Instrument: Family Distress in Advanced Dementia Scale
  - b. Zarit Burden scale, short form

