### **Electronic Health Record Review:**

1. Symptom assessment and management plans during hospitalization-
  - a. Palliative Care Domain Index Items
2. Documented discussion of dementia prognosis
3. Documented discussion decision-making for goals of care
4. New nursing home transfers
5. Return to acute care – ED or Hospital readmissions within 60 days and up to 3 reasons for return

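### No listed assessment records hospital and ED use before the index admission, and the primary model does not adjust for it: a low-cost chance to gain precision

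*Combined protocol and SAP*

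**What the plan says.** The primary endpoint (section 3) is the "Number of emergency room visits + hospital admissions within 60 days after discharge from index hospitalization". Section 9.4.2 compares arms by Poisson regression with robust standard errors, a follow-up offset and "main effects for treatment group, study site, GDS Stage and patient and caregiver sex as biological variables". The model has no term for earlier hospital or ED use.

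Every listed item on hospital or ED use looks forward from the index stay:

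- Schedule of Activities (1.2): the row "Hospital / ED transfers" is marked at the 30-day interview, the 60-day interview and the post-60-day EHR review. It is blank at Visit 1.
- Caregiver interviews (8.1): "Emergency room visits + hospital admissions after discharge from index hospitalization".
- EHR review (8.1): "reviews encompassing the 60-day period post-hospitalization", with the item "ED or Hospital readmissions within 60 days and up to 3 reasons for return".

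Visit 1 does include an "Enrollment Baseline Assessment", but its items are not listed. Before enrollment, "Site-CRCs will conduct brief chart reviews under a HIPAA waiver to confirm eligibility criteria" (5.3).

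Section 9.4.1 has a general rule for other baseline variables. Those found unequal between arms enter an initial model and stay only if removing them appreciably changes the treatment coefficient. Prior use is not named.

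**The concern.** Earlier counts of the same event are the natural baseline for a count outcome and a plausible predictor of it. Site, GDS stage and sex do not measure a patient's own history of hospital use. If that history predicts later transfers, leaving it out keeps explainable variation in the standard error of the IRR.

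The rule in 9.4.1 does not fill the gap. It screens for confounding, not prognostic value, so a balanced but strongly prognostic variable would not enter the model. A variable that was never collected cannot be checked for imbalance.

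At stake is power on the primary endpoint, where the plan's margin is thin. In the overdispersed row of Table 3, three of the four power values are below 0.80. The plan already looks for efficiency elsewhere: one stated attraction of the MZIP sensitivity analysis is a possible modest gain in power.

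**Working it through.** **Inputs.** Table 3: control rate 0.53; differences 0.25 and 0.20, so intervention rates 0.28 and 0.33. Section 9.2: two-sided alpha 0.05; 180 per arm (15% dropout) and 159 per arm (25% dropout). The documents do not state the overdispersion factor or any correlation between prior and later transfers.

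**Step 1: reproduce the Poisson row.** SE(log IRR) = sqrt(1/(n·λ1) + 1/(n·λ2)). For 0.53 vs 0.28 and n = 180:

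- SE = sqrt(1/95.4 + 1/50.4) = 0.174
- z = |ln(0.28/0.53)|/0.174 = 0.638/0.174 = 3.66
- power = Φ(3.66 − 1.96) = 0.956; Table 3 gives 0.96

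The other cells give 0.82, 0.93 and 0.77 against 0.82, 0.95 and 0.79. A rate-difference formula comes closer in those last two cells (0.94 and 0.78). No stated figure is called into question.

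**Step 2: recover the overdispersion factor φ.** Power = Φ(z/√φ − 1.96). For power 0.81, φ = (3.66/(1.96 + 0.878))² ≈ 1.67. Solving each of the four overdispersed cells gives 1.67 to 1.68. The single value 1.67 returns 0.81, 0.60, 0.76 and 0.55, exactly as in Table 3.

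**Step 3: add a prior-use covariate.** Suppose it removes a share s of the extra-Poisson part, so φ = 1 + 0.67(1 − s). The values of s are assumptions.

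| s | φ | n=180, diff 0.25 | n=180, diff 0.20 | n=159, diff 0.25 | n=159, diff 0.20 | Equivalent extra dyads |
|---|---|---|---|---|---|---|
| 0 | 1.67 | 0.81 | 0.60 | 0.76 | 0.55 | – |
| 10% | 1.60 | 0.83* | 0.62 | 0.78 | 0.57 | 4% |
| 20% | 1.54 | 0.84 | 0.64 | 0.79 | 0.58 | 9% |
| 40% | 1.40 | 0.87 | 0.68 | 0.83 | 0.62 | 19% |

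*0.825 before rounding. The last column is 1.67/φ − 1.

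**Step 4: check by correlation and simulation.** Let ρ be the correlation of the covariate with the 60-day count, and replace φ by φ(1 − ρ²). At n = 180 and difference 0.25, power is 0.81 at ρ = 0.1, 0.83 at 0.2, 0.84 at 0.3 and 0.91 at 0.5. Gamma-Poisson simulations with robust standard errors (3,000 runs per setting) agree in direction and rough size. At ρ about 0.29, power went from 0.83 to 0.87 for the 0.25 difference and from 0.62 to 0.65 for the 0.20 difference. At ρ = 0 there was no material change.

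**The case against.** The strongest reply is that the plan is valid as written, its power table does not rely on such a covariate, and the size of the gain is assumed. That stands. Four further points limit the claim.

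- **Prior use may be collected.** A reader might infer from the blank Visit 1 cell that it is not. The documents do not support that. The data-collection rows list outcomes only, and none is marked at Visit 1. The Charlson index, needed for eligibility in GDS 5, has no row either.
- **The source of the overdispersion is unknown.** A reader might infer that it reflects lasting differences between patients. The plan does not say so. More than 60% of pilot patients having no transfers is not evidence for it: a plain Poisson count gives exp(−0.53) = 59% zeros at the control rate and exp(−0.28) = 76% at the lower Table 3 rate, 67% averaged over both. An episode counted as both an ED visit and an admission would also raise the variance, and prior use would not remove that part.
- **GDS stage may already explain some of it.** Section 4.3 reports that all pilot transfers occurred in GDS 5–6. As an illustration, with equal thirds by stage and none in GDS 7, stage alone contributes 1/(1/0.53 + 1/0.28) = 0.18 of the 0.67 excess. If 1.67 is the unadjusted factor, the planned model has φ ≈ 1.49 and power of about 0.85 and 0.81. Removing 10–20% of the remainder then adds only 1 to 2 points at 180 per arm.
- **Chance imbalance is not a separate harm.** A reader might infer that an imbalance in frequent users biases the IRR. Randomization and the standard error already allow for it.

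What survives is that the model omits a plausible predictor, 9.4.1 would not admit it when balanced, and including it costs little.

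**Conclusion.** The point holds as an optional precision improvement. On the items listed, prior hospital and ED use is not recorded, and whether or not it is collected at enrollment, the primary model does not use it. With φ of about 1.67 taken as the variance left after planned adjustment, and 10% to 40% of the excess removed, power for the 0.25 difference rises by about 2 to 6 points at 180 per arm and 2 to 7 at 159. If GDS stage already accounts for part of the excess, or the correlation is 0.2 or less, the gain is 1 to 2 points or less. The documents do not settle where in this range the trial lies. They do not support reading the omission as a bias, an error in Table 3 or a threat to the planned analysis.

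**What to change.** 1. Record the number of ED visits and hospital admissions in a fixed look-back window before the index admission, excluding the index stay. Use one enrollment-interview question plus EHR abstraction after consent and before randomization. The screening chart review should not be the source, because its stated purpose under the waiver is to confirm eligibility. Add a Visit 1 entry to the schedule. If the enrollment assessment already contains the item, say so.
2. Name the count, for example as log(1 + count), among the covariates of the primary model in 9.4.2, whatever balance is observed and outside the change-in-effect rule. Fix the window and functional form before unblinded data are seen.
3. For dyads already enrolled, abstract the same pre-admission window during the planned post-60-day EHR review. Section 6.3 holds that review until after the 60-day interview because the chart shows palliative care encounters, and opening charts sooner could unmask the interviewer.

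The cost is a few minutes of coordinator time per dyad, one data field, one question and one covariate. Visits outside the site's health system will be under-counted. That reduces the gain but does not bias the comparison, because the window precedes randomization.
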